#### 3D Echo for evaluation of LV mass

3D Echo has demonstrated incremental value about LV mass over conventional echocardiographic modalities (M-mode, 2D Echo) in different patient populations [1,2]. The major strength of 3D Echo is the accurate imaging of cardiac structures avoiding the need for geometric assumptions in order to calculate outcomes such as the mass of the left ventricle.

Conventional echocardiographic modalities are limited mainly by inaccuracies and variations caused by use of geometric assumptions in case of asymmetric LV geometry and unintended use of oblique planes. 3D Echo, based on the assessment of a larger number of tomographic views, resolves these limitations. 3D Echo correspondingly has the advantage of reducing dependence on geometric models and reducing error based on angulated images [3, 4]. Thus, 3D Echo offers LV mass determination substantially comparable to cardiac magnetic resonance (CMR) imaging, as for global LV volumes [5]. This correlation between 3D Echo and CMR has also been stronger than that has been between conventional echocardiography and CMR [6]. Interobserver variability of real-time 3 dimensional echocardiography

(RT3DE) was additionally reported to be significantly lower than that of 2D Echo, supporting its superiority [7]. 3D Echo accuracy, has been verified using autopsy findings [4]. 3D Echo and CMR also produce comparable results in terms of LV mass with similar interobserver variability [8]. Moreover, 3D Echo is less dependent on operator practice and help to compensate operator inexperience when compared to conventional echocardiography.

3D Echo is feasible in the clinical setting and provides fast and accurate assessment of LV mass, which is superior to conventional echocardiographic methods, especially in distorted hearts. This leads to greater sensitivity and reduced sample size. As 3D Echo is less costly than CMP, it is modality of choice for the proposed study.

#### iii. Phlebotomy - laboratory examinations (See Appendix II)

Participants will undergo laboratory testing and related procedures according to standard of care for monitoring of patient with Rheumatoid arthritis on arthritis medications. Part of the blood obtained will be for usual patient care and part for research purposes as shown in the list below. The exact distribution of testing according to the visit can be viewed in Appendix II.

For study visit I standard of care tests and procedures will not be duplicated if they have already been performed prior to study entry and if results are available in patients records.

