## 2. STUDY DESIGN AND STATISTICAL PROCEDURES

### 2a. Study Design

(this section includes references)

For aim 1, the proposed studies will be performed in 150 patients with RA and 15 subjects without RA who will function as controls. The 150 patients will be recruited from the rheumatology clinics at New York Presbyterian Hospital of the Columbia University. The 15 control subjects will be recruited from the internal medicine clinics at the same institution or among friends of the recruited RA patients.

The 150 participants should have RA fulfilling established diagnosed criteria and not have a history of cardiovascular disease as indicated in the section for inclusion/exclusion criteria

[figure not shown]
These patients (150) will undergo the evaluations shown in the table below - and in more detail in Appendices I, II and III - during an initial visit (Visit I).

Evaluations	Visit I September/2011 - August/ 2014
Cardiac PET-CT scan*	X
3D Echocardiogram & CV Questionnaires	X RA X
Joint examination	X
Phlebotomy	X
Anthropometry	X
DEXA scan (body composition)**	X

\*including 3 transverse CT slices (mid-chest, L4-L5, mid-thigh) and cardiac CT for evaluation of coronary artery calcification (CAC).

\*\*only for the 50 participants who will be recruited for aim 2. (see below)

During the first PET scan a cardiac CT scan will be obtained in order to quantify coronary artery calcium (Agatston Score). Three additional CT Slices will be obtained (mid chest, lumbar, and mid thigh) to evaluate for visceral fat

accumulation as a risk factor for cardiovascular disease.

Controls will undergo only the PET-CT scan, 3D Echo, anthropometry evaluations, phlebotomy, and will complete abbreviated cardiovascular related questionnaires as outlined in Appendices I, II and III.

The PET-CT scan will occur on the same day or within one week of Study visit I.

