As already mentioned, the goal of this study is to investigate the "low LV mass phenotype" in patients with RA and its contributors in an attempt to elucidate the pathophysiology pathways that may connect RA with alterations in the myocardium and the evolution to heart failure. 3D-Echo will be used to measure the LV mass. Cardiac PET-CT imaging will be used to evaluate myocardial function (cardiac output, ejection fraction), microvasculature function (myocardial perfusion) and myocardial inflammation (F18-FDG uptake).

The research questions to be addressed with the study visit I are the following:

- i) Are anti-CCP antibodies or other RA-specific characteristics (e.g., disease duration, activity, severity) associated with lower LV mass (or other LV parameters of structure/function)?
- ii) What is the prevalence, the degree and correlates of microvascular dysfunction in RA? Is it associated with low LV mass or reduced global or regional contractility? Is it associated with systemic, articular and/or myocardial inflammation?
- iii) What are the prevalence, patterns, distribution and severity of inflammation as measured by F18-FDG uptake in myocardial PET imaging? Are intensity and/or distribution of F18-FDG uptake correlated with low LV mass or global or regional contractility? Does the severity/distribution of F18-FDG uptake correlate with levels of systemic and/or articular inflammation?

For the second aim of this study the goal is to evaluate the effect of TNF inhibitors on the myocardium. For the 50 patients undergoing randomization and the controls the questions to be addressed will be the following:

- i) Are global measures of LV structure (e.g., mass) or contractility (e.g., ejection fraction) affected (reduced or increased) by treatment with TNF antagonists? Is there a different effect compared to alternative therapy?
- ii) If microvascular dysfunction and/or inflammation are present before treatment, do they improve with treatment with TNF compared to alternative treatment? If parameters improve only with TNF inhibitor, this would suggest that TNF inhibitors exert a local anti-inflammatory effect on the myocardium mechanistically different compared to alternative treatment.
- iii) If treatment-induced improvements in microvascular dysfunction and/or inflammation (F18-FDG uptake) are

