observed with TNF inhibitor treatment and not with alternative treatment, do they correlate with (or mediate) global (or regional) changes in LV structure or function? If so, this would suggest a causal relationship between regional myocardial vasculopathy and/or inflammation with LV dysfunction.

iv) Do treatment-induced improvements in systemic inflammation (e.g., CRP) and RA disease activity correlate with changes in myocardial microvascular perfusion and/or inflammation? If so, this would suggest a relationship between systemic and myocardial inflammation.

In preliminary exploratory data analyses, summary statistics for the continuous and categorical variables will be calculated, including means, standard deviations, quartiles and ranges, and for the categorical variables, counts and percentages. In initial analyses, statistical comparison of continuous variables will be conducted using the t-test or nonparametric method, as appropriate. The comparisons of the prevalence of categorical CV risk factors will be conducted using the Chi-square test or the Fisher's exact test, as appropriate. All comparisons will be conducted at the  $\alpha=0.05$  level of significance using two-tailed tests, unless otherwise noted. To account for the potential for multiple comparisons artifact: a) First, significance testing will be based on a priori hypotheses and not spurious significant p-values; b) Second, if multiple comparisons are undertaken, adjustments in the threshold for statistical significance will be made as necessary. If multiple and collinear variables are detected, appropriate techniques will be utilized to minimize the impact of collinearity on the statistical efficiency of the derived parameter estimates.

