Linear mixed effects (MIXED) regression models will be used to assess trends in LV structure and functional outcomes over time between the two visits for the patients who will undergo randomization reevaluation with PET-CT and 3D Echocardiogram, while controlling for potential confounders. The data will include PET-CT studies for 25 RA patients receiving TNF antagonists and 25 RA patients receiving alternative treatment, and PET-CT studies for 15 non-RA patients. The data are longitudinal since LV outcomes are measured for each person at 2 different time points. Since repeated measures tend to be correlated within a person, mixed models with both fixed and random effects will be used to adjust for this correlation. We will use unstructured correlation structure given that each visit will occur roughly around a fixed time since study visit I, and use robust standard error estimates to conduct statistical inferences. To study the TNF inhibitor effects on LV structure or functional outcomes, visit-specific indicators, RA status, TNF treatment status, and visit x TNF treatment interaction will form the bases for the mean model. The visit-specific indicators will capture the time trend of LV outcomes over the study period, the RA status will delineate the overall mean difference in LV outcomes between RA and non-RA, with the TNF treatment status indicator and its interaction with visit indicators capturing the baseline difference in LV outcomes between TNF treated and non-treated groups and the potential TNF treatment effect on LV outcome over time, respectively. Actual TNF inhibitor dosage could be used in place of TNF status indicator in the model if necessary, and other potential covariates could be added into the model for confounding adjustment. For example, inflammation markers could be added into the model to examine whether any TNF treatment effect is mediated through the change in systemic inflammation. Similar modeling approaches can be used to study all research questions of interest using the corresponding outcomes and their hypothesized predictors listed in those questions to be addressed. For any binary outcomes in this type of regression analysis, e.g. indicator of whether a LV outcome exceeding certain critical value, generalized linear mixed effects models (GLIMMIX) can be used to study the odds of such outcome as a function of the independent variables.

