#### OTHER PROCEDURES THAT ARE CONSIDERED STANDARD OF CARE

(this section includes references)

Urine pregnancy test during every study visit involving radiation exposure (prior to the imaging and on the same day)  
PPD placement (1) for latent tuberculosis  
Pneumococcus vaccination (1)  
Influenza (seasonal and H1N1) vaccination (1)  
Ophthalmologic examination prior or within one year from initiation of treatment with Plaquenil (hydroxychloroquine) according to standard of care, as Plaquenil may rarely cause retinal toxicity (1)

As noted earlier this procedures will not be duplicated if they have taken place as part of usual care prior to participation in the study.

The total volume of blood for the purely research tests is 65 ml in study visits. In addition labs as part of usual care will add 21.4 ml of blood draw volume in Study Visit I and 9.4 ml in study visit II. The maximum amount of blood to be drawn including both research and usual care tests (at visit I) will be 86.4 ml in study visit I and 74.4 ml in study visit II. 9.4 ml of blood will be drawn in safety visits.

Blood samples for research purposes will be stored in Rheumatology divisional freezers at Columbia University in a de-identified manner indicated only by a numeric patient ID.

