#### Major Exclusion Criteria

For patient participation in Visit I (150 participants):

Prior self-reported physician diagnosed CV event (MI; angina; stroke or TIA; HF; prior CV procedure (e.g., coronary artery bypass graft, angioplasty, valve replacement, pacemaker);

Contraindications to having a PET-CT scan or receive adenosine or FDG.

Active treatment for Cancer

For patient participation in the randomized treatment and follow up visits (50 of the 150 initially enrolled participants):

Uncontrolled hypertension

Diabetes

Smoking

Treatment with a TNF inhibitor or other biologic currently or within the last 6 months

Treatment with any non-biologic DMARD other than MTX in the past two months;

Untreated positive PPD or active tuberculosis

History of Lymphoma and Melanoma

Ejection Fraction (EF) < 40% (if not known in advance then the Study Visit I Echocardiogram results will be used to exclude the patient in this part of the study)

Change with NSAID/Prednisone dosage in last 2 weeks

Participation in other research studies involving imaging/radiation exposure

A copy of the Patient Screening Form is attached to the protocol as Appendix XXV.

For controls :

Prior self-reported or physician diagnosed CV event (MI; angina; stroke or TIA; HF; prior CV procedure (e.g., coronary artery bypass graft, angioplasty, valve replacement, pacemaker);  
 Contraindications to having a PET-CT scan or receive adenosine or FDG.  
 Uncontrolled hypertension.  
 Participation in other research studies involving imaging/radiation exposure

A copy of the Control Screening Form is attached to the protocol as Appendix XXVI and a copy of the Radiation Screening Form is attached as Appendix XXVII.

RA subjects and controls who do not consent to any aspect of the study such as to the blood draws or to evaluation with PET-CT will be excluded from this study.

In addition patient and controls who are receiving treatment for cancer, with cognitive inability will be excluded from the study.

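### Baseline CRP and ESR may be taken from earlier chart results with no stated age limit, so they need not be concurrent with the Visit I PET-CT

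*Combined protocol and SAP*

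**What the plan says.** Section 3, part iii, gives the rule for the first visit: "For study visit I standard of care tests and procedures will not be duplicated if they have already been performed prior to study entry". The one further condition is "and if results are available in patients records". The rule is worded as a direction and states no time window. It refers to Appendix II for the distribution of tests by visit.

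The regular-care laboratory list that follows mixes two kinds of test. RF, CCP antibodies, G6PD and hepatitis serology change little or not at all. CRP, ESR, blood count, metabolic panel and fasting lipids vary over time. The rule does not separate them.

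Systemic inflammation is an analysis variable in three places in Section 2a:
- Visit I, question iii: "Does the severity/distribution of F18-FDG uptake correlate with levels of systemic and/or articular inflammation". Question ii asks the same of microvascular dysfunction.
- Aim 2, question iv: "Do treatment-induced improvements in systemic inflammation (e.g., CRP) and RA disease activity correlate with changes in myocardial microvascular perfusion and/or inflammation".
- The mixed-model plan: "inflammation markers could be added into the model to examine whether any TNF treatment effect is mediated through the change in systemic inflammation".

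The imaging side is dated closely: "The PET-CT scan will occur on the same day or within one week of Study visit I". Visit II has a window of 2 weeks either side of week 24.

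**The concern.** The cross-sectional questions relate a scan to a level of inflammation, so the two should describe the same moment. Under the rule as written, a coordinator who finds a CRP in the chart does not draw another, whatever its date. The scan is held to a week and the blood marker to nothing.

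The medication criteria do not close the gap. Entry to the randomised part requires a stable methotrexate dose for 6 weeks and stable NSAID and prednisone doses for 2 weeks (Section 6, Inclusion Criteria). A CRP older than those periods may predate a dose change. The criteria for the 150 Visit I patients contain no stability requirement.

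Two analyses are exposed. In aim 1, an old CRP or ESR is a predictor measured with error, and its associations shrink toward zero. In aim 2, the CRP change would start at an unspecified past date, so any change before study entry is counted in a quantity the plan calls treatment-induced. The mediation analysis uses the same change. Old lipid values could also weaken the adjustment for conventional cardiovascular risk factors.

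**Working it through.** **Inputs from the plan (Section 2b).** N = 150, two-sided alpha 0.05, 80% power, detectable correlation 0.227. This is a general figure for any two continuous variables at Visit I, not one specific to CRP.

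**Assumed inputs, not in the documents.** f is the share of patients with a reused result (25%, 50% and 100% shown). ρ is the correlation between the reused and a same-day value (0.5 to 0.9 shown).

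**Step 1: reproduce the plan's figure.** By Fisher's z, power = Φ(atanh(r)·√(N−3) − 1.96). With r = 0.227, atanh(r) = 0.231 and √147 = 12.124. The product is 2.801, and Φ(2.801 − 1.960) = Φ(0.841) = 80.0%. The minimum detectable r is tanh((1.960 + 0.842)/12.124) = 0.227. A simulation of the t-test for r also gave 80.0%. The figure stands when predictor and outcome are concurrent.

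**Step 2: attenuation.** Suppose reused and same-day values have the same mean and SD, reuse is unrelated to the outcome, and the old value relates to the scan only through the current one. The observable correlation is then r·k, with k = (1 − f) + f·ρ. Example: f = 0.5 and ρ = 0.7 give k = 0.85, observable r = 0.193 and power 65.9%.

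| Share reused | ρ | k | Power at true r = 0.227 | True r needed for 80% power |
|---|---|---|---|---|
| none | – | 1.000 | 80.0% | 0.227 |
| 25% | 0.9 | 0.975 | 77.9% | 0.233 |
| 25% | 0.7 | 0.925 | 73.4% | 0.245 |
| 25% | 0.5 | 0.875 | 68.5% | 0.259 |
| 50% | 0.9 | 0.950 | 75.7% | 0.239 |
| 50% | 0.7 | 0.850 | 65.9% | 0.267 |
| 50% | 0.5 | 0.750 | 55.0% | 0.303 |
| 100% | 0.9 | 0.900 | 71.0% | 0.252 |
| 100% | 0.7 | 0.700 | 49.3% | 0.324 |
| 100% | 0.5 | 0.500 | 28.2% | 0.454 |

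**Step 3: the CRP change in aim 2.** Let X0 be the reused value, X1 the same-day baseline and X2 the Visit II value, all with unit variance. Let corr(X0, X1) = ρ, corr(X1, X2) = c and corr(X0, X2) = cρ. The correlation between the change computed from the reused value and the true 24-week change is

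(1 − c − cρ + ρ) / √[(2 − 2c)(2 − 2cρ)].

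With c = 0.2 and ρ = 0.7 this is 1.36/√(1.60 × 1.72) = 0.82. For ρ from 0.5 to 0.9 the range is 0.71 to 0.94 at c = 0.2, and 0.61 to 0.91 at c = 0.5. Both values of c are assumptions for CRP. These figures apply to a patient group in which every baseline is reused.

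**Step 4: is Visit II different?** The reuse rule names Visit I only. Usual-care blood is 9.4 ml at Visit II and 9.4 ml at safety visits, and the interim safety panel includes CRP and ESR (Section 12, Safety assessments). A fresh Visit II CRP is therefore a fair inference, although no Visit II list by test name is in the text reviewed.

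**The case against.** The strongest reply is that the rule may be meant for one-off screening items. Section 3 budgets 21.4 ml of usual-care blood at Visit I against 9.4 ml at Visit II. That is 12.0 ml more, which fits a full panel being drawn at baseline. Phlebotomy is scheduled for everyone at Visit I, and Appendix II might require a CRP there. This is a fair reading of intent. It does not remove the point, because the rule as written covers the whole regular-care list and the 86.4 ml total is described as a maximum. It does limit confidence about how often reuse would happen.

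Other parts of the reply also stand. Joint counts and CDAI are assessed at each study visit, so a concurrent measure of articular inflammation remains. Research blood (65 ml) is stored at study visits and could supply a same-day CRP later, although the plan commits it only to future biomarker work.

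Four stronger readings are tempting, and the documents do not support them:
- A reader might infer that baseline CRP values will be months old. The text permits this; nothing shows it will happen.
- A reader might infer that the randomised comparison is biased. Reuse depends on records made before randomisation and should be balanced between arms. The LV outcomes do not use CRP, and CDAI is built from joint counts and patient and physician ratings.
- A reader might infer that chart timing could produce a false positive answer to question iv. That would need pre-study CRP drift to track later change on PET, and no mechanism for this is shown.
- The same reuse rule covers other procedures: "As noted earlier this procedures will not be duplicated if they have taken place as part of usual care prior to participation in the study". These include the PPD test, so a reader might add it to this concern. PPD enters no inflammation analysis and is not part of the point.

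**Conclusion.** The concern holds in limited form. The available text allows baseline CRP, ESR and fasting lipids of any age, while the baseline scan is fixed to within a week of Visit I. The expected effect is attenuation of the aim 1 associations with systemic inflammation, and contamination of the aim 2 CRP change and mediation analysis by change before study entry.

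The size cannot be fixed from the documents. With a quarter of values reused at agreement 0.9, the loss is about 2 percentage points of power. With half reused it is about 4 to 25 points across agreement 0.9 to 0.5. The 28% figure is a worst case that needs every patient reused at agreement 0.5, and should not be read as a forecast. The conclusion is also conditional on Appendix II not already setting a window or requiring these tests at Visit I.

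**What to change.** Amend the sentence in Section 3, part iii, so that reuse applies only to tests that do not vary materially over time, such as G6PD, hepatitis serology, and RF and CCP on the same assay. Require CRP and ESR from the Visit I blood draw, before randomised treatment starts. Require fasting lipids from the same draw if they are used as covariates. Align Appendix II with this wording.

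The cost is a one-sentence amendment and some repeat routine assays. No extra venipuncture is needed, because Visit I phlebotomy takes place for everyone. The stated Visit I maximum already includes the usual-care tubes (65 + 21.4 = 86.4 ml). Participants attend study visits fasting (Section 11), so fasting lipids can be drawn then.

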#### LABS TO BE PERFORMED AS PART OF REGULAR CARE

Rheumatoid factor

CCP antibodies

Complete blood count with differential (CBC)

Comprehensive metabolic panel (CMP)

CRP (CRP), ESR

Fasting lipid panel

G6PD

HCV Ab  
HBVsAg and HBVsAb

#### LABS FOR PURELY RESEARCH PURPOSES

Blood for processing, storage, and future biomarker evaluation

#### OTHER PROCEDURES THAT ARE CONSIDERED STANDARD OF CARE

(this section includes references)

Urine pregnancy test during every study visit involving radiation exposure (prior to the imaging and on the same day)  
PPD placement (1) for latent tuberculosis  
Pneumococcus vaccination (1)  
Influenza (seasonal and H1N1) vaccination (1)  
Ophthalmologic examination prior or within one year from initiation of treatment with Plaquenil (hydroxychloroquine) according to standard of care, as Plaquenil may rarely cause retinal toxicity (1)

As noted earlier this procedures will not be duplicated if they have taken place as part of usual care prior to participation in the study.

The total volume of blood for the purely research tests is 65 ml in study visits. In addition labs as part of usual care will add 21.4 ml of blood draw volume in Study Visit I and 9.4 ml in study visit II. The maximum amount of blood to be drawn including both research and usual care tests (at visit I) will be 86.4 ml in study visit I and 74.4 ml in study visit II. 9.4 ml of blood will be drawn in safety visits.

Blood samples for research purposes will be stored in Rheumatology divisional freezers at Columbia University in a de-identified manner indicated only by a numeric patient ID.

